4.1 General Parameters

Collected variables included age, body mass index (BMI), intraoperative blood loss, operative duration, and length of postoperative hospitalization.

4.2 Safety Parameters

Laboratory and clinical assessments—including complete blood count, electrocardiography, and liver function tests—were performed preoperatively (upon admission), on the day of surgery before treatment, and on postoperative Day 5.

Adverse events related to acupuncture were monitored during treatment, such as syncope, needle breakage, bending or retention, palpitations, and excessive perspiration.

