2.3 Study Objective

To explore the clinical efficacy and safety of abdominal acupuncture therapy in promoting gastrointestinal function recovery after gynecological laparoscopic surgery.

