2.4.3.3 Abdominal acupuncture treatment

The initial abdominal acupuncture treatment was performed 4–6 hours after surgery, followed by one session daily from postoperative day 1 through day 4, yielding a total of five sessions per treatment course. Throughout the treatment period and thereafter, patients' clinical conditions were systematically recorded and evaluated, with concurrent monitoring of adverse events and concomitant medication use.

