4.3.3 Relevant Assessment Scales

- **Pain assessment:** The Visual analogue scale (VAS) was applied (Appendix 1). Abdominal pain scores were recorded before and after treatment on the day of surgery (5 days after surgery).
- **Gastrointestinal symptom assessment:** Symptom scoring was based on the Perioperative Clinical Evaluation Standards for Gastrointestinal Motility (Guangdong Provincial Standard, Appendix 2). Scores were documented daily from the day of surgery (before treatment) through postoperative Days 1–5, according to observed gastrointestinal function.
- **Quality of life assessment:** The Gastrointestinal Quality of Life Index (GIQLI) was employed (Appendix 3). Assessments were performed on the day of surgery prior to treatment, on postoperative Day 5, and again on Day 14 following the final treatment session.

5. Adverse Events and Management

If adverse reactions occurred during the trial—such as needle stagnation, syncope, breakage, hematoma, or infection—investigators promptly managed the event, ensured patient safety, reassured the participant with an explanation, and documented the details in the case report form.

6. Ethical Principle

This clinical trial was reviewed and approved by the Ethics Committee of Guangdong Provincial Hospital of Traditional Chinese Medicine prior to participant enrollment (Approval No. YF-2023-435-01). The study was conducted in full compliance with the principles of the Declaration of Helsinki.

7. Statistical Analysis

Data were organized and managed using Microsoft Excel to establish a primary database, which was subsequently converted into an SPSS 26.0 database for statistical analysis. The Shapiro–Wilk test was employed to assess the normality of continuous variables. According to data distribution, descriptive statistics were presented as mean \pm standard deviation (SD) for normally distributed variables, and as median with interquartile range [P₂₅, P₇₅] for non-normally distributed variables. Between-group comparisons of normally distributed data were performed using independent-samples t tests, while within-group pre- and post-treatment comparisons were conducted using paired t tests. For non-normally distributed data, the Mann–Whitney U test was applied for between-group comparisons, and the Wilcoxon signed-rank test for within-group comparisons.

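### As worded, section 4.2 covers acupuncture-related events during treatment, leaving all-cause adverse events with no stated collection in the control arm

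*Protocol*

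**What the plan says.** Section 2.3 makes safety part of the aim: "To explore the clinical efficacy and safety of abdominal acupuncture therapy".

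Three places then describe adverse events, and they differ:

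- Section 4.2, Safety Parameters: "Adverse events related to acupuncture were monitored during treatment", with syncope, needle faults, palpitations and sweating as examples. This limits both cause (acupuncture) and time (treatment).
- Section 5, Adverse Events and Management, deals with adverse reactions during the trial, "such as needle stagnation, syncope, breakage, hematoma, or infection", and has them documented in the case report form.
- Section 2.4.3.3, Abdominal acupuncture treatment, has patients' condition recorded during the treatment period and afterwards, "with concurrent monitoring of adverse events and concomitant medication use". It sets no limit on cause, but it sits under the acupuncture heading.

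Section 4.2 also schedules blood count, ECG and liver function tests, which "were performed preoperatively (upon admission), on the day of surgery before treatment, and on postoperative Day 5". No arm is singled out. Section 2.4.5 gives the control group standard care, with no needling.

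**The concern.** An event that must be related to acupuncture to count cannot, by definition, be counted in a patient who receives none. Yet several of the protocol's own examples (syncope, palpitations, sweating, hematoma, infection) do not need a needle to occur and can follow a hysterectomy. Only a concurrent control count, collected in the same way, can show whether acupuncture adds to them. The rule also requires an event to be attributed to needling before it counts, when a randomized comparison would let the arms themselves supply the attribution.

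At stake is the safety half of the objective. A statement that acupuncture is safe in this setting would rest, for these events, on a one-arm list of reactions.

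**Working it through.** The protocol states no figure on this point, so the check sets its sections side by side.

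**1. Which named events could occur without a needle?** Sections 4.2 and 5 together name needle breakage, bending, and retention or stagnation, which are needle-specific. They also name syncope, palpitations, sweating, hematoma and infection, which are not. That leaves five event types for which a control count would be informative.

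**2. What is collected without restriction to one arm?**

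- Section 4.2: blood count, ECG and liver tests at three time points. Two of these precede treatment, so only the Day 5 reading can show a difference arising after it.
- Section 4.3.1: distension or pain, nausea, vomiting and diarrhea, recorded daily to Day 5 or discharge, whichever is earlier. These are classed as efficacy.
- Section 4.3.3 with Appendix 2: the symptom scale, scored daily through Day 5, which includes incision status and the highest temperature of the day.
- Section 7: chi-square or Fisher tests between groups for categorical data, which could be applied to any counts collected in both arms.

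**3. Matching 1 against 2.**

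| Event not needing a needle | Stated control-arm record |
|---|---|
| Syncope | none |
| Palpitations | none as an event; ECG at fixed times only |
| Sweating | none |
| Hematoma | none as an event |
| Infection | partial: incision signs and temperature |

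Four of the five have no stated control-arm record as events, and the fifth has a partial one.

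**4. Serious adverse events.** Sections 2.4.2.7 and 2.4.3.5 mention them for any patient, but as grounds for ending participation. Neither section is a rule for recording them by arm over a defined period.

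**5. Does section 2.4.3.3 close the gap?** Its sentence has no limit on cause and runs beyond the treatment period. Read generously, it could cover both arms. Read by its heading, it covers acupuncture patients. Either reading conflicts with section 4.2, which is narrower in cause and in time. Nothing in the protocol says which governs.

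**The case against.** The strongest reply is that safety data are not missing from the control arm. Laboratory tests and ECG are scheduled as safety parameters with no arm limit. Gastrointestinal complications, incision status and temperature are recorded in the same way, and between-group tests are provided. The list in section 5 is illustrative and includes events other than needling faults. Section 2.4.3.3 monitors adverse events without a relatedness limit, and the trial-flow section in which it stands has no separate control-arm step, so its heading may not be meant to exclude controls.

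Much of this stands, and it rules out two stronger readings. A reader might infer that adverse events are collected only as acupuncture reactions; section 2.4.3.3 does not support that. A reader might also infer that there is no control-arm safety comparison at all; the laboratory, ECG, complication and symptom-scale data contradict that. A further inference, that staff who know the allocation screen out events judged unrelated, is not supported either. The protocol does not say who judges relatedness or when, or that unrelated events are discarded.

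What the reply does not supply is a statement that all-cause adverse events are recorded in both arms over a common window. Nor can this be left to a statistical analysis plan that is not shown. Such a plan can choose how to compare events, but it cannot recover events that the protocol did not require to be recorded.

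**Conclusion.** The point holds in this form: section 4.2 restricts adverse events to acupuncture-related ones during treatment, section 5 mostly follows it, and section 2.4.3.3 differs from both in scope and window. As written, the between-arm safety comparison is confined to blood count, ECG and liver tests, complications classed as efficacy, and the incision and temperature items. Syncope, palpitations, sweating, hematoma and infection away from the incision have no stated control-arm collection.

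The conclusion assumes that section 4.2, as the safety section, governs what is recorded. If practice followed the general reading of section 2.4.3.3 in both arms, the data may exist and only the text needs correcting. The documents give no event rates, so no bias or loss of precision can be calculated. The analysis of time to first flatus is not affected. The change is worth making because safety is a stated objective.

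**What to change.** Reconcile sections 2.4.3.3, 4.2 and 5 so that they state one rule:

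- Record all adverse events and serious adverse events, whatever their presumed cause, in both arms.
- Use one common window: surgery to Day 5 or discharge, plus the final GIQLI contact. Section 4.3.3 times that contact from the last treatment session, so the protocol should state the matching date for controls.
- Assess relatedness after recording, not as a condition for it.
- Report counts by arm, with needling-specific reactions listed as a treated-arm subset.

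The cost is a little more recording, about one case report form page used in both arms. Most of the contacts already exist, although daily observation under section 4.3.1 can end at discharge before Day 5.

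Section 2.4.2.1 gives enrollment from December 2023 to December 2024, and the text is largely in the past tense, so collection may be over. In that case, extract inpatient events for both arms from hospital records by the same procedure. Otherwise, limit the safety conclusion to acupuncture reactions in the treated arm and the laboratory and ECG comparison.

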3.2.2 Acupoint Selection

Acupoint selection for abdominal acupuncture was based on Abdominal Acupuncture Therapy¹⁴:

Primary points: Zhongwan (CV12), Xiawan (CV10), Qihai (CV6), Guanyuan (CV4), and bilateral Daheng (SP15).

Secondary points: bilateral Huaroomen (ST24) and Wailling (ST26).

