3.2.4 Procedure

Patients were placed in the supine position with the abdominal region fully exposed. Acupoint selection and needling techniques followed the standards outlined in *Abdominal Acupuncture Therapy*. For localization: the distance from the umbilicus (CV8) to Zhongting (CV16) was defined as 8 cun above the navel; from the umbilicus to the pubic symphysis was defined as 5 cun below the navel; and the transverse distance from the umbilicus to the lateral abdominal margin was defined as 6 cun. All acupoints were measured precisely with a straight ruler and proportionally located. After strict hand hygiene and aseptic preparation of the acupoint sites,

routine skin disinfection was performed. Disposable sterile acupuncture needles were inserted perpendicularly. Care was taken to ensure minimal or no pain during insertion. Needle manipulation employed gentle rotational techniques without lifting or thrusting. Primary acupoints were needled to the *Di level* (deep layer, at the base of subcutaneous fat or on the fascia, insertion depth approximately 1.0–1.5 cun), primarily for treating visceral disorders. Secondary acupoints were needled to the *Ren level* (intermediate layer, within the mid-fat tissue, insertion depth approximately 0.5–1.0 cun), predominantly for stimulating peripheral systems. Needle depth was adjusted according to body habitus, and patients were not required to experience the typical *deqi* sensations of soreness, numbness, distension, or heaviness.

Needles were retained for 30 minutes, during which an infrared therapeutic lamp was applied for concurrent warming therapy. After treatment, needles were withdrawn carefully, and sterile cotton was applied with gentle compression at the insertion sites to prevent bleeding.

Note: Needling was avoided directly at surgical incisions. In such cases, acupoints were either slightly displaced for adjusted localization or omitted as appropriate.

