4.3 Efficacy Parameters

4.3.1 Clinical efficacy indices

- **Recovery of gastrointestinal motility** including time to first postoperative passage of flatus (recorded to the exact hour and minute), time to first postoperative bowel movement (recorded precisely), and restoration of bowel sounds.
- **Incidence of postoperative gastrointestinal dysfunction** related complications: including abdominal distension or pain, nausea, vomiting, and diarrhea.

All the above parameters were observed starting on the day of surgery and continued to be

recorded daily until the fifth postoperative day or discharge, whichever came first.

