Nausea	 10 points: No nausea	 5 points: No nausea at rest, mild nausea upon activity	 0 points (i) Intermittent nausea at rest  0 points (ii) Persistent nausea at rest with aggravation during activity		
Vomiting	 10 points: None	 5 points: 1–2 episodes/day	 0 points (i) 3–5 episodes/day; 0 points (ii) ≥6 episodes/day		
Diarrhea	 10 points: None	 5 points: 1–2 episodes/day	 0 points (i) 3–5 episodes/day; 0 points (ii) ≥6 episodes/day		
Surgical Incision	 10 points: Well-approximated, without redness, swelling, or pain	 0 points: Redness, swelling, heat, pain, fat liquefaction, or wound dehiscence			
Body Temperature	°C	 10 points: ≤37.5°C	 5 points: 37.5–39°C	 0 points: ≥39°C (Record highest temperature of the day)	
7:00-9:00	Time: ____ h ____ min	 10 points	 5 points	 0 points	 Not recorded
11:00-13:00	Time: ____ h ____ min	 10 points	 5 points	 0 points	 Not recorded
17:00-19:00	Time: ____ h ____ min	 10 points	 5 points	 0 points	 Not recorded
Time of first tolerance to food	Semi-liquid diet	 None	 Yes: ____ h ____ min		
	Solid diet	 None	 Yes: ____ h ____ min		

Appendix 3

Gastrointestinal Quality of Life Index

Please mark √ in the box corresponding to the option that best applies to you, for example: E.

Scoring Criteria: A = 0 points, B = 1 point, C = 2 points, D = 3 points, E = 4 points.

The sum of all item scores constitutes the GIQLI total score.

Total Score: _____

1. During the past week, how often have you experienced abdominal pain (frequency and severity)?
 A. All the time B. Most of the time C. Sometimes D. Occasionally E. Never
2. During the past week, how often have you experienced a sense of gastric (epigastric) fullness or distension?

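### Section 4.2 restricts its adverse-event outcome to events attributed to acupuncture, which un-needled controls cannot have, so that outcome supports no comparison between arms (minor; cheap to improve)

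*Protocol*

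**What the plan says.** Protocol 2.3 sets out to explore the "clinical efficacy and safety of abdominal acupuncture therapy". Section 4.2 (Safety Parameters) has two parts. The first is blood count, ECG and liver function at three time points, with no mention of cause or arm. The second is the adverse-event outcome: "Adverse events related to acupuncture were monitored during treatment, such as syncope, needle breakage, bending or retention, palpitations, and excessive perspiration".

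Adverse events also appear elsewhere in the protocol:

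- 2.4.3.3, within the description of the acupuncture course, has adverse events and concomitant medication monitored, without limiting them to acupuncture.
- 2.4.2.5 makes haematoma, skin damage or rash at the primary points a reason for dropout.
- 2.4.2.7 ends participation for serious adverse events or complications that prevent continuation.
- Section 5 has adverse reactions, including haematoma and infection, documented in the case report form.

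Two items that bear on harm sit in the symptom scale of Appendix 2, which 4.3.3 lists under efficacy: "Scores were documented daily from the day of surgery (before treatment) through postoperative Days 1–5". The incision item gives 10 points for a clean wound and otherwise "0 points: Redness, swelling, heat, pain, fat liquefaction, or wound dehiscence". The temperature item carries the instruction "Record highest temperature of the day" and gives 10, 5 or 0 points. Neither item asks for a cause, and neither is restricted to one arm.

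**The concern.** An event related to acupuncture can arise only in patients who are needled. An outcome defined that way has a control count fixed at zero before any patient is enrolled, so the difference between arms reflects the definition and the investigator's judgement of cause, not the randomised comparison.

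For needle breakage or a bent needle this does no harm, because the cause is obvious. It matters for events that surgery and needling can both produce. After a laparoscopic hysterectomy, a red wound or a fever often cannot be assigned to one or the other in a single patient. If it is put down to surgery, it drops out of the 4.2 outcome. If it is put down to needling, it stands there with no control rate beside it. A concurrent control arm exists to settle that question, and the 4.2 wording does not use it.

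**Working it through.** **1. The texts side by side.**

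| Place | Scope of adverse events | Can controls contribute? |
|---|---|---|
| 4.2, adverse-event sentence | Related to acupuncture; all examples are needling events or acute reactions | No |
| 4.2, laboratory tests and ECG | No attribution limit | Yes |
| 4.3.2, CRP, IL-6, TNF-α, SII | No attribution limit | Yes |
| 2.4.3.3 | Adverse events in general, but placed in the acupuncture section | Not excluded by the wording |
| Section 5 | Adverse reactions; all examples are needling events or infection | Unclear |
| Appendix 2, incision and temperature | No attribution | Yes |

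The protocol is therefore inconsistent about scope: 4.2 is narrow and 2.4.3.3 is broad. The narrow wording is the one under the safety heading.

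**2. Exposure (3.2.2 and 3.2.5).** CV12, CV10, CV6 and CV4 give 4 points. Bilateral SP15, ST24 and ST26 give 2 each. So 4 + 2 + 2 + 2 = 10 per session, and 10 × 5 sessions = 50 insertions per patient at most. On points that meet a wound, 3.2.4 says: "Needling was avoided directly at surgical incisions. In such cases, acupoints were either slightly displaced for adjusted localization or omitted as appropriate". This explains why wound and febrile events are worth counting. It is not evidence that needling causes them.

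**3. What the control count changes.** The documents give no wound or fever rates, so the counts here are assumed; n = 38 per arm is the enrolment target in 2.4.4. Suppose 4 of 38 acupuncture patients have an event (4/38 = 10.5%). Under 4.2 the acupuncture count may be anything from 0 to 4, depending on attribution, and the control count is 0 whatever happens to controls.

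With all-cause counts, use the Newcombe interval for d = p1 − p2, built from the Wilson limits (l, u) of each arm:

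- lower = d − √[(p1 − l1)² + (u2 − p2)²]
- upper = d + √[(u1 − p1)² + (p2 − l2)²]

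For 4 of 38, l = 0.042 and u = 0.241. For 0 of 38, l = 0 and u = z²/(n + z²) = 3.84/41.84 = 0.092. For 4 v 0:

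- lower = 0.105 − √(0.064² + 0.092²) = −0.006
- upper = 0.105 + 0.136 = 0.241

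| Acupuncture v control | Risk difference, points (95% CI), 38 per arm | 33 per arm |
|---|---|---|
| 4 v 4 | 0.0 (-15.0 to 15.0) | 0.0 (-16.9 to 16.9) |
| 4 v 1 | 7.9 (-4.7 to 21.7) | 9.1 (-5.2 to 24.5) |
| 4 v 0 | 10.5 (-0.6 to 24.1) | 12.1 (-0.6 to 27.3) |
| 0 v 0 | 0.0 (-9.2 to 9.2) | 0.0 (-10.4 to 10.4) |

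The same acupuncture-arm record reads as no difference or as a possible excess, depending on a control count that the 4.2 outcome does not supply.

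**4. Whether a test would help.** Exact power of Fisher's two-sided 5% test at 38 per arm is 0.037 for an assumed 5% v 10%, and 0.164 for 5% v 15%. The comparison can only be descriptive.

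**The case against.** The strongest reply is that listing procedure-specific events is legitimate. The sentence in 4.2 does not say that other events go unrecorded, and which recorded items are tabulated by arm is ordinary content for a statistical analysis plan, which is not at hand. Much of this stands. The absence of a wound or fever table is not in itself an error, and Section 7's chi-square or Fisher rule could be applied to both items. Scoring incision and temperature within the cited provincial scale is not an error either.

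What the reply does not remove is the 4.2 wording itself. The protocol has stated its adverse-event outcome there, and the statement is one that only one arm can meet. A later table would not correct that definition or its mismatch with 2.4.3.3.

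Three stronger readings are tempting and are not supported:

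- *That the trial has no control-arm safety data.* Laboratory tests, ECG and inflammatory markers are not restricted to one arm.
- *That wound or febrile events are lost.* Incision and temperature are scored daily whatever the cause, and Section 5 documents infection.
- *That needling near incisions endangers wounds.* The documents give no rate, and 3.2.4 requires aseptic preparation, skin disinfection and sterile single-use needles.

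It is also fair to say that the incision item is a weak measure of wound harm, because pain alone scores 0.

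**Conclusion.** The point holds in a limited form. The 4.2 adverse-event outcome depends on attribution, is in effect a one-arm outcome, and does not match the broader monitoring in 2.4.3.3, so as written it supports no comparison of adverse events between arms. This is a minor point about definition and reporting. It does not touch time to first flatus or any efficacy conclusion.

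Its size cannot be measured from the documents. The table above rests on assumed counts and on 38 (or 33) patients per arm with records; every interval in it includes zero. It shows why a control count is needed. It does not show that an excess of harm exists or that this trial could detect one.

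**What to change.** Reword 4.2 to this effect: adverse events are reported by arm for all randomised patients, whatever their attribution; needling-specific events (syncope, needle breakage, bending or retention, and the like) are listed separately for the acupuncture arm.

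Then add one descriptive table by arm for Days 1 to 5, separate from the symptom score:

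- **Temperature.** Patients with a daily highest value above 37.5 °C, and at or above 39 °C, with risk difference and 95% CI. Take these from the recorded °C value, because the point bands on the form share their boundaries at 37.5 and 39.
- **Incision.** Patients scored 0, reported as the whole box, with a note that it mixes pain with wound signs. Split it only if existing clinical notes allow.
- **Days observed per arm.** The 4.3.1 records run "recorded daily until the fifth postoperative day or discharge, whichever came first". If these items also stop at discharge, unequal stays would bias the counts. Keep dropouts in up to their last record.

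The cost is a few lines and one small table, with no new visit, test or patients. The downsides are wide intervals, low-grade fever that is non-specific after surgery, and skin that may be warm or red after the infrared lamp. Section 2.4.2.1 gives enrolment to December 2024; if it has ended, the table should be labelled post hoc.
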